5.3 Individuals

All Robson group I women giving birth at the included birth care units during the study period will adhere to the allocated guidelines for labour progression, which the birth care unit is randomised to.

5.3.1 Informed consent

All nulliparous women planning to give birth at any of the included birth care units will receive written information about the trial from the midwife in antenatal care, when called for routine ultrasound, at the ultrasound control or at the labour ward. Eligible women will be asked to sign an informed consent permitting her data to be included in the analyses and to answer a questionnaire on childbirth experience, four weeks after birth. All nulliparous women will have a trial sticker put on the antenatal record to make identification easier on admission for assessing Robson group affiliation.

5.3.2 Baseline data

- Age
- Height
- Prepregnant weight
- Civil status
- Education
- Smoking
- Gestational age at onset of spontaneous labour

5.4 Guideline instruction and local coordinators

The PI will introduce the allocated guideline to each cluster. At each cluster, one person responsible for the trial at the specific birth care unit (local coordinator) will be designated. The local coordinator is responsible for inclusion of participants, record control of each participant and for the local implementation of the trial. The local coordinators will act as contact persons to PI, and they must report any challenges to her.

5.5 Procedures for Discontinuation

5.5.1 Cluster Discontinuation

The reason for discontinuation of included clusters will be recorded. Clusters who withdraw from the trial after randomisation will be sought replaced by an equivalent cluster.

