4 OVERALL STUDY DESIGN

4.1 Hypothesis

We hypothesise that adhering to the guideline for labour progression presented by [name] (21) (figure II) will decrease the rate of emergency caesarean sections and augmentation with oxytocin among low-risk nulliparous compared to adhering to guidelines for labour progression based on a modified Friedman's curve (3) (figure I), without jeopardising the outcome for mother or neonate.

In this multicenter trial we include 14 birth care units Norway. Each cluster will be randomly allocated to either intervention or control arm.

Intervention - Labour progression guideline in the intervention clusters (Zhang's guideline, Z):

During established first stage of labour, i.e. regular painful contractions and cervical dilatation ≥ 4 cm (1), dystocia is diagnosed if the cervix dilatation rate does not meet the expected progression according to Zhang's findings (Appendix A). During second stage of labour, dystocia is diagnosed, if the time from full dilatation to active expulsion phase (passive second stage) exceeds 1 hour and 45 minutes (2 hours and 30 minutes for women with epidurals), or if the expulsion phase (active second stage) exceeds 60 minutes. This progression curve is based on contemporary research on labour progression by [name] (Appendix A).

Control - Labour progression guideline in the control clusters (based on Friedman's guideline, F): During established first stage of labour, i.e. regular painful contractions and cervical dilatation from 4 cm (1), dystocia is diagnosed if cervix dilatation rate is less than 1 centimetre per hour assessed after 4 hours (crossing the 4-hours action line). During second stage of labour, dystocia is diagnosed if the time from full dilatation to active expulsion phase (passive second stage) exceeds exceeds 1 hour (2 hours for women with epidurals), or if the expulsion phase (active second stage) exceeds 60 minutes.

The randomisation process will be performed through a central computer assisted programme which stratifies by number of deliveries and the rate of caesarean sections for Robson group I at each unit per year. The trial will be conducted according to the CONSORT statement for planning and implementation of cluster randomised trials (23).

We believe that cluster randomisation, i.e. randomisation at hospital level, is superior to individual randomisation as choosing individual randomisation for this specific study would imply substantial risk of contamination.

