8.2 Randomisation

8.2.1 Allocation-sequence generation

Key elements to specify regarding allocation of treatment are:

- The method of generating the allocation sequence is computer-generated
- The allocation ratio is equal to one
- The type of randomisation is restricted
- The factor; size of birth care unit and rate of emergency caesarean sections will be used for stratification

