8.4 Statistical Analysis

The analyses will be conducted according to the principle of intention-to-treat to estimate the effect of assigned guideline. The difference between groups will be presented with a risk ratio (RR) and a 95 % confidence interval (95% CI). For dichotomous efficacy variables a significance test taking into account the cluster structure of the data will be used (25). In the case of a substantial lack of adherence due to missing data, also 'as treated' or 'per protocol' analyses will be performed to estimate the effect of used guideline, after appropriate adjustment via inverse probability weighting or g-estimation (26,27).

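### Section 5.5.1 provides for replacing clusters that withdraw after randomisation but describes no random allocation of the replacement; counting it in place of the withdrawn cluster would conflict with intention-to-treat

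*Protocol*

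**What the plan says.** Protocol section 5.5.1 has two sentences on clusters that leave. The first is "The reason for discontinuation of included clusters will be recorded". The second is "Clusters who withdraw from the trial after randomisation will be sought replaced by an equivalent cluster". The section does not define equivalence, say who selects the replacement, describe how its arm is assigned, or say what happens to the withdrawn unit's data.

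The design treats the birth care unit as the thing randomised. Section 4.1 says "In this multicenter trial we include 14 birth care units Norway" and "Each cluster will be randomly allocated to either intervention or control arm". Section 8.2.1 describes a computer-generated sequence and adds "The allocation ratio is equal to one" and "The type of randomisation is restricted". On the stratification factors it says "size of birth care unit and rate of emergency caesarean sections will be used for stratification".

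Section 8.4 commits the analysis: "The analyses will be conducted according to the principle of intention-to-treat to estimate the effect of assigned guideline". Nothing in the protocol text at hand reconciles the replacement rule with that commitment.

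**The concern.** In a cluster trial the comparison is protected by the random assignment of units, and here there are only 14. The guideline is introduced openly at each unit (section 5.4), so a unit that leaves after randomisation can do so knowing its arm. If its place is then filled one for one, the newcomer's arm is settled by which unit left and not by chance.

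Entry is exposed in the same way. Under section 3.3 a unit joins only if it is willing to follow its allocated guideline. A replacement for a vacated place can know which guideline that is before it agrees. Section 5.2 has all eligible units invited at the outset, so a replacement would probably be one that first declined, answered late or became eligible later.

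If exit or entry depends on attitude to a known guideline, and that attitude is related to caesarean practice, the arms differ for a reason other than the guideline. Matching on size and past caesarean rate would not remove selection on willingness. The weighting and g-estimation named in section 8.4 are aimed at departures from the assigned guideline, not at exchanging the randomised units.

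**Working it through.** **Reading the sections together**

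1. Sections 4.1 and 8.2.1: 14 clusters at 1:1 gives 14/2 = 7 per arm.
2. Section 5.5.1: a cluster leaves and another is sought for its place. Returning to 7:7 requires the newcomer to enter the vacated arm.
3. Section 8.4: the analysis is by assigned guideline. The withdrawn cluster has a random assignment; the newcomer, on the reading in step 2, has none. An analysis that swaps one for the other does not compare the units as randomised.

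**The plan's own sample size**

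Inputs from sections 3.2 and 8.1: p1 = 0.092, p2 = 0.069, significance level 0.05 (taken as two-sided), power 80%, 14 clusters, 6582 women, so n = 6582/14 = 470.1 per cluster. I assume the cited formula is the usual unmatched form for two proportions, in clusters per arm:

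c = 1 + (1.960 + 0.842)² × [p1(1−p1)/n + p2(1−p2)/n + k²(p1² + p2²)] / (p1 − p2)²

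The protocol does not give k, the between-cluster coefficient of variation, so 14 clusters cannot be confirmed from its inputs. Solving for c = 7 gives k = 0.083 (0.0825 before rounding):

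- [0.083536 + 0.064239]/470.1 = 0.000314
- k²(p1² + p2²) = 0.00681 × 0.013225 = 0.000090
- c = 1 + 7.849 × 0.000404/0.000529 = 7.0

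This k is used below as an assumption. The point about randomisation does not depend on it.

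**Effect of one replacement on an arm's rate**

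With equal cluster weights, shift = d/7, where d is the difference in underlying caesarean rate between the departed and the replacement unit. The documents give no d, so a range is assumed. The planned difference is 9.2 − 6.9 = 2.3 points.

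| d (points) | Shift (points) | Share of 2.3 |
|---|---|---|
| 1 | 0.14 | 6% |
| 2 | 0.29 | 12% |
| 3 | 0.43 | 19% |
| 4 | 0.57 | 25% |

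Section 3.2 allows larger units to contribute more women, so in an analysis weighted by women a large unit would count for more than 1/7 and a small one for less.

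**How plausible is d?** Take two unmatched units at the 9.2% rate. At k = 0.083 the between-unit SD is 0.083 × 9.2 = 0.76 points and the SD of a difference is 0.76 × √2 = 1.08 points. A 4-point gap is then 4/1.08 = 3.7 SDs, which is extreme. At k = 0.25 the SD of a difference is 0.25 × 9.2 × √2 = 3.25 points, and 4 points is 1.2 SDs, which is ordinary.

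**Cost of not replacing a lost cluster**

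Using the same approximation with one cluster subtracted per arm, variance = [p1(1−p1)/n + k²p1²]/(c_control − 1) + [p2(1−p2)/n + k²p2²]/(c_intervention − 1), and power = Φ[(p1 − p2)/√variance − 1.96]. At k = 0.083:

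| Clusters (intervention/control) | Power, 470 per cluster | Power, total held at 6582 |
|---|---|---|
| 7/7 | 80% | 80% |
| 6/7 | 77% | 79% |
| 7/6 | 76% | 78% |
| 6/6 | 72% | 77% |

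For 6/7, for example: 0.000235/6 + 0.000169/5 = 0.0000730; 0.023/0.00855 = 2.69; Φ(2.69 − 1.96) = 0.77. For k from 0 to 0.25 at 470 per cluster, losing one cluster costs between about 2 and 5 points of power, although the starting power itself varies widely with k.

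**The case against.** The strongest reply is that section 5.5.1 governs recruitment and section 8.4 governs analysis. Seeking another unit to restore numbers is compatible with intention-to-treat if the departed unit stays in its arm and the newcomer is handled separately. The 1:1 statement describes how the sequence is generated and does not strictly require a final 7:7. An equivalent unit could mean one matched on the stratification factors. Units must be willing to follow whichever guideline they draw (3.3), sign a cooperation agreement (5.2.1) and have their management's agreement (10.2), all of which make withdrawal less likely.

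Much of this stands, and it limits what can be claimed. A reader might infer that replacements would be hand-picked, that the departed unit's data would be discarded, that units are likely to leave because of the arm they drew, or that intention-to-treat is already broken. The protocol says none of these. It names no selector, is silent on the departed unit's data, and gives no evidence on why units might leave. Nor is a shift in an arm's rate bias in itself: it can go either way, and becomes systematic only if exit or entry is related to the known arm.

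What the reply does not remove is the stated rule. It provides for replacement after randomisation, describes no random step, and most naturally means filling a vacated place. An SAP, which was not available, could exclude replacements from the primary analysis, but it could not make a substituted unit randomised. The text between sections 2.2 and 3.2 was not available either, so a clarification there cannot be ruled out.

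**Conclusion.** The point holds as a conflict between a stated conduct rule and the randomisation and intention-to-treat commitments. It is conditional: there is no harm unless a cluster withdraws after randomisation, is replaced, and the replacement is counted in its stead. If that happens, 14% of an arm's clusters are not randomised, and matching on size or caesarean rate does not restore randomisation.

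The shift of 6% to 25% of the planned effect rests on an assumed 1 to 4 point difference and equal weights. Its upper end should not be presented as typical unless between-cluster variation is well above k = 0.083. Nor should one assume that two replacements double the shift, which is true only if both differ by the same amount in the same direction. The rule should be settled in advance, because a decision taken after a withdrawal would be taken knowing the arm.

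**What to change.** Replace the rule in section 5.5.1 with two statements:

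- Every randomised cluster remains in its allocated arm in the primary analysis, with all data that consent permits.
- Any unit added after allocation is known enters only a labelled sensitivity analysis. If added units are meant to count in the primary analysis, they are randomly allocated, for example in pairs within stratum, and do not displace the withdrawn cluster.

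Aggregate study-period counts from a withdrawn unit could support a further sensitivity analysis but should not be written into the primary one. Section 10.3 requires documented consent before any participant's data are analysed, and section 13 gives each hospital ownership of its data. Such counts would also cover all Robson group I women, whereas other units contribute only those who consented.

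The cost is a change of protocol wording and a small, visible loss of power if a cluster leaves: from 80% to about 76–77% for one cluster at the assumed k = 0.083 and 470 women per cluster, or about 78–79% if the remaining units enrol enough to keep the total at 6582.

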5.5.2 Trial Discontinuation

The trial may be discontinued at the discretion of the trial manager in the event of any of the following:

- Occurrence of adverse events unknown to date in respect of their nature, severity and duration
- Medical or ethical reasons affecting the continued performance of the trial
- Difficulties in the recruitment of clusters or individuals

The trial manager and PI will inform all investigators, the relevant Competent Authorities and Ethics Committees of the termination of the trial along with the reasons for such action.

6 ASSESSMENTS

6.1 Consecutively Assessments

Consecutively assessments e.g. vaginal explorations, fetal monitoring and interventions will be conducted throughout labour.

6.2 Safety Assessments

All Robson group I women in both arms will be cared for and monitored according to the procedures at each birth care unit. Necessary interventions due to the mother's or the fetus' needs, will be conducted regardless of the allocated guidelines for labour progression.

7 DATA MANAGEMENT AND MONITORING

7.1 Data collection during delivery

At each labour ward the midwife on duty will identify Robson group I women and make sure that the allocated guideline is followed. During labour the midwife responsible for the labour care, keeps record as usual in the electronic medical record and on paper when it comes to Zhang's guideline. For all women with a signed consent who have allowed their data to be included in the trial, the local coordinator will fill in the web-CRF.

7.2 Web-Case Report Forms (Web-CRFs)

Due to different systems for electronic medical records, and due to additional handwritten records, a web-based case report form (web-CRF) is being designed by the Unit of Applied Clinical Research at the Faculty of Medicine at the Norwegian University of Science and Technology, (NTNU). The web-CRFs will be a web-based programme accessible to the local coordinators which will enter all variables. Each participant will be registered by their inclusion number. The system will generate the inclusion number depending on which local coordinator that is logging in, to ensure that the inclusion number is unique. The inclusion numbers will indicate unit and local inclusion number. The web-CRFs are transferable to statistical programmes, such as STATA and SPSS. All clusters will get access to the web-CRF with boxes for all required information.

The local coordinators will ensure that the data required from the protocol is entered into the web-CRF, that the data are complete and accurate, and that entry is performed in a timely manner. She will also ensure that each woman is eligible for the trial before entering her data in the web-CRF. The signature of the local coordinators will attest the accuracy of the data on each web-CRF. If any assessments are omitted, the reason for such omissions will be registered in the web-CRF. Also subsequent corrections in the reporting in web-CRF, including the reason for the corrections, will be recorded. (See appendix E for information on the web-CRF from NTNU).

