2.1 Primary Endpoint

The rate of emergency caesarean sections

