8 STATISTICAL METHODS AND DATA ANALYSIS

8.1 Determination of Sample Size

The determination of the sample size (number of clusters and individuals for analysis) is based on a power calculation with the least occurring primary outcome; emergency caesarean section, which is 9.2 % in the study population (p1). Further, we expect that the emergency caesarean section rate will be 6.9 % (p2) when using the new guideline for labour progression.

Formula (4) on page 320 in the article by Hayes et al. (24) is used to calculate the needed number of clusters and participants. According to this formula, with a chosen significance level of 0.05, a power of 80 % and p1=9.2 % and p2=6.9 %, we will have to include at least 14 clusters using the allocated guideline in 6582 Robson group I women.

All statistical analysis will be conducted in STATA, SPSS or similar statistical software.

In the 14 clusters there will be approximately 8000 women fulfilling the inclusion criteria per year (2012). With an expected inclusion of 90 % and a dropout of 10%, the required numbers of women should be included within 10-12 months.

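### The last eligibility decision is made at web-CRF entry by the local coordinator, who knows the arm, with no required log or reconciliation of consented women left out

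*Protocol*

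**What the plan says.** The protocol describes two eligibility steps.

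- **On the ward (Section 7.1).** "At each labour ward the midwife on duty will identify Robson group I women". She must also see that the unit's guideline is followed. Section 5.3.1 helps her with a trial sticker on the antenatal record of every nulliparous woman.
- **At data entry (Section 7.2).** The local coordinator fills in the web-CRF for consenting women, and "She will also ensure that each woman is eligible for the trial before entering her data in the web-CRF".

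Section 5.4 describes the coordinator's role: "The local coordinator is responsible for inclusion of participants, record control of each participant and for the local implementation of the trial". Each unit follows a single guideline (Section 4.1), so she knows the allocation.

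The primary endpoint is "The rate of emergency caesarean sections" (Section 2.1). The variables to be collected include Apgar score, umbilical artery pH, and NICU transfer and length of stay (Section 2.2).

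On records, Section 10.4 asks for a list of included participants. Section 7.2 asks for reasons when assessments are omitted or entries corrected, which concerns women already in the database. Section 10.3 has signed consents filed at the site and scanned into the medical record.

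**The concern.** The second step decides who is analysed. It is taken by someone who knows the arm and has a stake in the guideline, and nothing in the text requires it to be taken before the mode of birth is known. The form cannot be completed until after the birth, and the record she works from would normally show how the woman delivered.

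If women with a caesarean are judged ineligible more readily in one arm than in the other, the primary rate shifts without any effect of the guideline. The analysis in Section 8.4 is by intention to treat, and the statistician in Section 8.3 works blind to group. Both safeguards act only on women in the database and cannot recover those never entered. The step also applies to women who have consented, so better consent procedures would not close it.

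**Working it through.** **Inputs from the protocol**

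- Emergency caesarean rates of 9.2% (control) and 6.9% (expected with the new guideline), Section 8.1. The planned difference is 9.2 − 6.9 = 2.3 points, and the planned risk ratio is 6.9/9.2 = 0.75.
- 14 units and 6,582 women (Section 8.1), allocated one to one (Section 8.2.1). 6,582/14 = 470.1, which reproduces the roughly 470 per cluster in Section 3.2. With an even split, each arm has 7 units and 3,291 women.

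**Assumed.** The documents do not say how many women would be excluded at data entry, or with what mode of birth. The cases below give a range. All take a true rate of 9.2% in both arms.

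**Case 1: only women with caesarean are left out, in intervention units only.** A unit of 470 has 470 × 0.092 = 43.24 caesareans. Leaving out x of them gives a rate of (43.24 − x)/(470 − x).

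| x per unit | Observed rate | Risk ratio against 9.2% | Share of the unit's caesareans |
|---|---|---|---|
| 4 | 39.24/466 = 8.4% | 0.92 | 4/43.24 = 9% |
| 6 | 37.24/464 = 8.0% | 0.87 | 6/43.24 = 14% |
| 11.6 | 6.9% | 0.75 | 11.6/43.24 = 27% |

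The last row solves for 6.9%: x = 470 × (0.092 − 0.069)/(1 − 0.069) = 10.81/0.931 = 11.6, which is 2.5% of the unit's women. Over the arm it is 3,291 × 0.023/0.931 = 81 women.

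**Case 2: partly selective exclusion in one arm.** If a share e of the arm is left out and those women have caesarean risk q, the rate becomes (0.092 − e·q)/(1 − e). With e = 5%:

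- q = 20%: 0.082/0.95 = 8.6%
- q = 30%: 0.077/0.95 = 8.1%
- q = 50%: 0.067/0.95 = 7.1%

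**Case 3: exclusion unrelated to outcome.** With q = 9.2%, the rate is 0.092(1 − e)/(1 − e) = 9.2%, whatever e is.

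**Case 4: the same selective exclusion in both arms.** With x = 4 in every unit, both arms show 8.4% and the risk ratio is 1.

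A false difference therefore needs exclusion that depends on the outcome and differs between arms. The losses in Case 1 (1% to 2.5% of women) would not stand out against the 90% inclusion and 10% dropout that Section 8.1 already expects.

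**The case against.** The strongest reply is that the protocol leaves means of finding women who were dropped. A consented woman who is not entered still has a signed form on file and in her record (Section 10.3). There are also the stickers, the ward identification and the questionnaire request to all Robson group I women (Section 7.3). Section 9.4 allows source data verification. This stands: a reader might infer that excluded women leave no trace, and that is not so. What the text lacks is a requirement to use these traces. Appendices C and E, on inclusion and the web-CRF, are listed but not in the text available here, so the point is limited to the body of the protocol.

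A reader might also take "The system will generate the inclusion number depending on which local coordinator that is logging in" to mean that a woman has no number until her outcome data are entered. The sentence explains how numbers are kept unique and says nothing about when they are issued.

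That the coordinator knows the mode of birth is an inference. Section 7.2 asks only for timely entry. The inference is strong, given what the form contains, but the protocol does not state it.

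Most of the Robson group I definition (parity, single fetus, presentation, gestation) is largely objective. Spontaneous onset is the item that leaves most room for judgement. This limits how many women could plausibly be reclassified, but does not remove the risk.

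Finally, the case that reproduces the whole planned effect is extreme. The figure of 2.5% of women looks small, but it means removing about 27% of all caesareans, in one arm only, with no vaginal birth excluded. Nothing in the documents suggests that this would occur.

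**Conclusion.** The point holds as a weakness in procedure. The final eligibility decision rests with a coordinator who knows the arm and is responsible for the guideline. It is taken at a step that in practice follows the birth, with no required log of consented women left out and no reconciliation. Outcome-related exclusion is possible in this open cluster trial, and the planned analysis would not correct it.

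The size depends wholly on assumptions about who is excluded. One-sided, caesarean-only exclusion of 4 per 470 women moves 9.2% to 8.4%, and about 12 per 470 moves it to 6.9%. Exclusion that is non-selective, or equal in both arms, produces no difference when there is none.

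The documents do not support saying that such bias occurs, or that it could not be detected. They support saying that the plan does not guard against it, and that a guard would cost little.

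**What to change.** Amend Sections 7.1 and 7.2 as follows.

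1. When the midwife on duty identifies a woman at the labour ward, she records the Robson items as then known: parity, plurality, presentation, onset and gestation.
2. The coordinator enters every consented woman so identified in the web-CRF, including those she believes ineligible.
3. Eligibility for analysis is derived from the recorded items by a prespecified rule, applied blind to arm and mode of birth. This replaces the coordinator's own decision.
4. The reason for each exclusion is recorded, and exclusions are reported by arm with mode of birth.
5. Filed consents are reconciled against web-CRF entries for each unit.

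The ward midwife still knows the arm, but she records the items before the mode of birth is known. Web-CRF access can stay with the coordinators. Issuing a web-CRF number at admission to every consenting nulliparous woman would need new access and would capture many ineligible women, so it is not proposed.

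The cost is a short extra record at identification and brief entries for women later ruled out. Section 7.2 describes the web-CRF as still under design, so the fields can be added now. No clinical care changes.
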